**Metformin, Vitamin D, and Depression in Polycystic Ovary Syndrome (PCOS)
Trial**

NCT03380091

Document Date: October 2, 2019

Metformin, Vitamin D, and Depression in PCOS (MINDD) Trial

PROJECT SUMMARY

The MINDD (Metformin, vitamin D, and Depression) pilot study will include 20 reproductive-age women with polycystic ovary syndrome (PCOS), insulin resistance, low Vitamin D, and depression. Subjects will be randomly assigned in a 1:1 ratio to either Vitamin D or metformin for 12 weeks. We will use standardized, validated questionnaires to assess depression, anxiety and quality of life. At baseline, 6 weeks, and at the completion of the protocol, we will assess the following measures: 1) Depression Severity, 2) Serum 25-hydroxyvitamin D level, and 3) HOMA-IR (Homeostasis Model Assessment of Insulin Resistance), which is calculated from fasting insulin and glucose. The aim is to determine whether treatment of insulin resistance OR vitamin D deficiency in women with PCOS, insulin resistance, low Vitamin D, and depression, improves mood symptoms.

HYPOTHESIS

We hypothesize that treatment of metabolic abnormalities, specifically insulin resistance or Vitamin D deficiency, in women with PCOS and depression, will improve mood symptoms.

OBJECTIVES

Primary Aims

1- To collect pilot data that examines changes in depression symptoms among women with PCOS and depression taking metformin

2- To collect pilot data that examines changes in depression symptoms among women with PCOS and depression taking Vitamin D

Secondary Aims

1- To collect pilot data that examines changes in anxiety symptoms and PCOS-related quality of life among women with PCOS and depression taking metformin or Vitamin D

2- To investigate a potential correlation between change in serum 25-hydroxy vitamin D and change in depression score, and HOMA-IR and change in depression score

DESIGN & METHODS

This is a single center, open-label, randomized, pilot clinical trial. Twenty-five subjects will be enrolled in order to have 20 subjects complete the study with roughly 10 subjects in each treatment regimen arm. Subjects will be randomly assigned in a 1:1 ratio to either Vitamin D3 (cholecalciferol) or metformin for 12 weeks. Evaluations will be completed at baseline, after 6 weeks, and after completing 12 weeks of treatment. Blood specimen collection and analysis will occur at baseline and after 12 weeks of treatment. Screening data will be reviewed to determine subject eligibility. Subjects who meet all inclusion criteria and none of the exclusion criteria will be entered into the study.

Total duration of subject participation will be 12 weeks. The following treatment regimens will be used:

- The Vitamin D group will receive 5,000 IU cholecalciferol (Vitamin D3) tabs once daily
- The Metformin group will receive 500 mg metformin once daily for the first week, 500 mg twice daily for the second week, and 1,000 mg twice daily for the duration of the 12-week trial.

Standard Survey Instruments

Beck Depression Inventory II (BDI-II),

State Trait Anxiety Inventory (STAI)

PCOS-related quality of life by the PCOS Quality of Life survey (PCOSQ)

International Physical Activity Questionnaire (IPAQ)

Blood specimen Assays

Blood specimens are assayed at Quest Diagnostics as part of routine clinical diagnostics, for participation in the UCSF PCOS Multidisciplinary clinic. This is a requirement for initial clinic intake, and the panel is

routinely repeated again after 3 months as part of clinical follow-up. These specimens are not stored but rather discarded after assay.

For those Clinic patients who did not have specimens assayed at Quest initially for these clinical baseline purposes, we will repeat the panel testing at Quest Diagnostics for consistency of assays for research purposes. Specimens are destroyed after assay and are not stored.

Inclusion Criteria

1. Female age 18-45
2. Documentation of a Polycystic Ovary Syndrome diagnosis by Rotterdam Criteria
3. Insulin resistance as evidenced by HOMA-IR > 2.0, calculated from fasting glucose and insulin
4. Mild or greater severity depression as evidenced by BDI-II > 14
5. Written informed consent obtained from subject and ability for subject to comply with the requirements of the study.

Exclusion Criteria

1. Currently receiving pharmacologic treatment for depression
2. Current metformin use of > 1gm daily
3. Current or recent (within prior month) Vitamin D supplementation, unless this preceded the lab confirming Vitamin D insufficiency
4. Insulin-dependent diabetes mellitus
5. Pregnancy or breastfeeding
6. Untreated hypothyroidism
7. Current active substance abuse
8. Other major medical comorbidity: renal or hepatic dysfunction, severe pulmonary disease
9. Presence of a condition or abnormality that in the opinion of the Investigator would compromise the safety of the patient or the quality of the data.

BACKGROUND

PCOS is the most common endocrinopathy in women, impacting 10-15%. Women with polycystic ovary syndrome (PCOS) are afflicted by depression at rates 4-8x that of their peers without PCOS, even when controlling for BMI (2, 3). Depression contributes to the burden of this disorder and impacts efforts at self-care. The cause of increased depression risk in PCOS is unknown, and there has been minimal investigation into underlying mechanisms. As a result, no targeted treatment strategies exist. Emerging evidence supports the paradigm that systemic metabolic disturbances act centrally to disturb mood. Metabolic derangements are common in PCOS, and hyperinsulinemic insulin resistance (IR) is core to the pathophysiology of the disorder. In addition, Vitamin D (Vit D) deficiency is prevalent and is associated with IR in PCOS. Indeed, in PCOS, we have shown that women with IR are at increased risk of depression compared to their non-IR peers, and similar findings have been suggested for Vit D deficiency, potentially due to a direct effect of Vit D on mood or due to its relationship with IR. However, it is not known if correcting either of these metabolic abnormalities will ameliorate depressive symptoms. We hypothesize that treatment of IR OR Vit D deficiency in depressed women with PCOS will improve mood. We propose to conduct a pilot open-label randomized trial to test our hypothesis.

We acknowledge potential concerns that delaying treatment for insulin resistance or Vitamin D insufficiency may negatively impact study participants. However, the primary well-established potential consequence of Vitamin D deficiency is reduced bone density with increased risk for osteoporosis with chronic deprivation over the course of many years. Thus, a 12-week delay in initiating Vitamin D treatment is not anticipated to negatively impact outcomes. Similarly, delay of 12 weeks for treatment of insulin resistance will not likely predispose to rapid development of diabetes mellitus, the primary indication for treatment. Further, we discuss diet and exercise interventions with all our patients; this is another established strategy for combatting insulin resistance. Because metformin and Vitamin D have not yet been shown to impact mood in PCOS, we cannot assume the short delay in initiating treatment with either medication will negatively affect quality of life in our patients. Indeed, this is the objective of our study, to establish a new targeted therapeutic approach, which requires a randomized study design. Finally, we suspect that increased medical attention and counseling obtained through study participation will overall offset any risks inherent in a 12-week delay in initiating Vitamin D or metformin therapy.

PRELIMINARY STUDIES

Insulin resistance is strongly associated with depressed mood. Emerging evidence suggests the peripheral metabolic milieu impacts brain function. "Metabolic syndrome type II", and "type 3 diabetes mellitus" describe the respective mood and cognitive disorders associated with impaired insulin signaling at the level of the brain. Diabetes doubles depression risk. Insulin resistance is a proposed mediator, based on epidemiologic data, animal studies and clinical trials.

Vitamin D deficiency is also associated with depressed mood. Observations studies have linked Vitamin D deficiency with depression risk specifically in PCOS. Clinical trial data in the general population has demonstrated antidepressant efficacy of Vitamin D in deficient persons with major depression.

Standard Clinical Practices

In our UCSF Multidisciplinary PCOS Specialty Clinic, patients have a panel of laboratory work prior to seeing us in two separate weekly sessions each month. During their visits, they have sessions with: 1) Reproductive Endocrinologists, 2) a Genetic Counselor, 3) a Dermatologist, 4) a Psychologist, and 5) a Registered Dietician. All patients undergo rigorous diagnostic assessment to confirm or rule out a diagnosis of PCOS. All patients receive counseling about the implications of a PCOS diagnosis - including insulin resistance and metabolic dysfunction, the importance of endometrial protection, fertility concerns and hyperandrogenic stigmata. All patients receive counseling about lifestyle interventions to manage their PCOS risks, such as diet and exercise strategies. They also are counseled about options for medical management of symptoms which concern them. Medications are prescribed through insurance. Three months following our initial clinic visits, the patients repeat their laboratory testing and return for a follow-up

visit to check in on how they are doing.

For women with PCOS and Vitamin D below 30 ng/mL, it is standard clinical practice to recommend Vitamin D supplementation. Provider practice varied historically with serum levels ranging from 20-30; however, the Endocrine Society does recommend supplementation at these levels and we are in agreement. Notably, in our PCOS clinic, which has been functioning for more than a decade, we only starting testing Vitamin D levels this year, as additional research implicates this Vitamin in a variety of potential health issues, although the primary indication for supplementation is bone health, a chronic process. Recent literature suggests that at least 2 in 3 women with PCOS are Vitamin D insufficient. The vitamin D dosing outside the context of this research trial may differ (i.e. weekly dosing rather than daily dosing). We selected daily dosing to more closely match the daily requirement of the Metformin group to take a medication, and the psychological outcome of interest which, which might benefit from a more closely matched daily reminder of intention. We would not routinely assess adverse side effects as we plan in this trial.

For women with impaired fasting glucose (i.e. fasting glucose > 100 mg/dL) or impaired glucose tolerance (i.e. 2-hour glucose level >140 mg/dL), standard clinical practice is to recommend insulin sensitizing interventions. Options include lifestyle interventions and metformin, which is the first line medication. For patients with insulin resistance as indicated by HOMA-IR, believed to be an early stage of impaired glucose tolerance, metformin is another option we discuss. The threshold HOMA cut-off varies; ours was selected given our prior research on the association between insulin resistance and depression risk. Recent evidence suggests that Vitamin D may have an insulin sensitizing role in diabetics; however, this is not definitive.

Thus, standard clinical practice in patients participating in our trial, who are insulin resistant, would be a combination of Vitamin D repletion and insulin sensitizing measures which can include a variety of lifestyle and metformin. All patients are thoroughly counseled about the importance of diet and exercise and thus all patients will have an intervention to improve insulin resistance. A possible 12-week delay in initiating Vitamin D treatment (if recommended), while outside of standard clinical practice, is not an urgent intervention. At the 3-month follow-up visit we check the status of IR and Vitamin D and prescribe treatments on that basis, ensuring close follow-up and addressing metabolic needs. Notably, the prevalence of Vitamin D insufficiency and IR is estimated at over 2 in 3 women with PCOS, most of whom are likely unaware of these conditions. Our close clinical attention and diagnostics overall with help offset risks imposed by these conditions if they exist chronically over years, primarily concerns regarding bone health and progression to pre-diabetes or diabetes.

STATISTICAL ANALYSIS PLAN

Sample Size Calculations: In our study, the primary outcome is change in BDI-II score (depression symptoms). A 3-point difference in BDI-II change is considered clinically significant (38). We determined expected change in BDI-II scores and standard deviations from prior studies of Vitamin D (14) and metformin (39). Using an alpha=0.05, power=0.80, and a 1:1 randomization scheme, we calculated a sample size of 8 per group, for a total of 16. Given a level of uncertainty with our assumptions on the basis of limited prior research, we aim to have 10 subjects per group complete the trial, for a total of 20. Assuming 20% attrition, we will recruit 25 subjects to result with 20 in total.

Statistical Analysis Plan: The primary endpoint is to investigate the effectiveness of the treatments on the BDI depression scores. The secondary endpoints are the change in HOMA-IR and 25(OH)D. These models will be adjusted for important covariates as needed such as BMI, age and baseline BDI-II as appropriate. Summary statistics will be provided and all testing will be performed at the 0.05 level of significance. Exploratory analyses will test for a relationship between change in HOMA-IR and 25(OH)D and depression scores.

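### Does admitting current metformin users of up to 1 g/day, with no written rule for background use, undermine the depression results?

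*Combined protocol and SAP*

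**What the plan says.** **Eligibility.** Exclusion Criterion 2 reads "Current metformin use of > 1gm daily". Criterion 3 excludes current or recent vitamin D supplementation "unless this preceded the lab confirming Vitamin D insufficiency". Criterion 9 adds discretion over any condition that "in the opinion of the Investigator would compromise the safety of the patient or the quality of the data".

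**Regimen.** Design & Methods states one schedule for the metformin arm: "The Metformin group will receive 500 mg metformin once daily for the first week, 500 mg twice daily for the second week", then the full dose for the rest of the 12 weeks. It has no separate text for women already on the drug.

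**Aims and visits.** Primary Aim 1 concerns "changes in depression symptoms among women with PCOS and depression taking metformin"; Primary Aim 2 is the same for vitamin D. On data collection, Design & Methods says "Screening data will be reviewed to determine subject eligibility" and "Evaluations will be completed at baseline, after 6 weeks, and after completing 12 weeks of treatment".

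**Rationale.** The Background section defends the design by arguing that waiting 12 weeks to start the drug not assigned is acceptable.

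**Analysis.** The Statistical Analysis Plan allows adjustment for important covariates, giving BMI, age and baseline BDI-II as examples.

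**The concern.** Read together, these sections leave the current user without a rule. It is not stated whether her metformin continues after randomisation, whether the trial regimen replaces or adds to it, or what happens to it if she is assigned vitamin D. The same question arises for vitamin D taken before the qualifying laboratory test. No medication item is listed for weeks 6 and 12.

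Both primary aims are within-arm changes. Randomisation balances background use between arms in expectation, but it does not protect a within-arm change from a treated baseline. A woman already on metformin may have less left to gain, and with about 10 completers per arm each woman carries 10% of the mean. Use during follow-up that nobody writes down cannot be reliably recovered later.

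**Working it through.** **1. Who can enter.** Criterion 2 does admit women at or below 1 g/day. Criterion 3 is less ambiguous than it looks. Its exception covers current as well as recent use, and current use cannot have ended before the test. For a current user it can only mean use that began before a test which still showed insufficiency. What stays open is whether that use continues, the same question as for metformin.

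**2. How many.** The documents give no count. Standard Clinical Practices says "metformin is another option we discuss" for insulin resistance, but that describes what is offered once the laboratory work-up is done. It is not evidence of treatment before entry. The only sign that current users are expected is that the exclusion criteria mention them.

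**3. What is said about follow-up.** The Background text on delay implies that the unassigned drug is not newly started. It is written as if neither drug had been started, which does not fit a woman admitted under Criterion 2. That is a conflict of wording, confined to continuing users.

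**4. Size.** Inputs from the Statistical Analysis Plan: 10 completers per arm, 3 BDI-II points as the clinically significant difference (used here only for scale), 8 per group at alpha 0.05 and power 0.80, and 20% attrition.

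- Recruitment reproduces: 20 / (1 − 0.20) = 25.
- The 8 per group cannot be reproduced, because no SD is printed. With a two-sided two-sample t-test it implies a standardised difference of 1.51. If the powered difference were 3 points (assumption), the SD would be 3 / 1.51 = 1.99.
- Shrinkage of the within-arm mean = (k / 10) × f × 3. Here k is the number of current users among 10 completers and f is the share of a user's change that is lost. At f = 0 nothing is lost; at f = 1 she shows no change from any cause. Values between need a dose-response that the documents do not give.
- 95% half-width = t(0.975, n − 1) / √n × SD. For n = 10 this is 0.715 SD: 1.43, 3.58 or 7.15 points at an assumed SD of 2, 5 or 10.

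| Users k of 10 | Shrinkage, f = 0 to f = 1 | Half-width at SD 2 |
|---|---|---|
| 1 | 0 to 0.30 points | 1.43 points |
| 2 | 0 to 0.60 points | 1.43 points |
| 4 | 0 to 1.20 points | 1.43 points |

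The f = 1 column is an extreme. There is no untreated arm, so the within-arm change also contains regression to the mean after entry at BDI-II > 14, attention and counselling, and open-label expectation. Prior use removes none of these. In the vitamin D arm, if a woman stopped metformin and lost a 3-point benefit, that arm's mean would move by 3 / 10 = 0.30 points, the same order.

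**5. Would a report without users help?** Dropping two of 10 widens the half-width from 0.715 to 0.836 SD, a factor of 0.836 / 0.715 = 1.17. With no users, the report repeats the main one.

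**6. What the analyst already has.** Criteria 2 and 3 cannot be applied without asking about both drugs, so baseline use is known for every woman. The covariate list is given by example and does not shut it out.

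**The case for a change.** The strongest case is that the gap is real and cheap to close. No section answers the question, Criterion 9 gives discretion and not a rule, and 25(OH)D or HOMA-IR cannot stand in for a medication record. Chance imbalance is likely too. If 4 of 20 completers were users (an assumption), the chance that the arms differ by two or more is 1 − C(4,2)·C(16,8)/C(20,10) = 1 − 77,220/184,756 = 0.58. On the between-arm scale, with a standardised effect of 1.51 and 10 per group, power would fall from 0.89 to 0.72 if 20% of participants contributed no treatment contrast.

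Part of this stands. The sections do not fit together for a continuing user, and follow-up use is best noted at the time. The figures carry less weight. The imbalance and power results both rest on a number of users that the documents do not supply. The power loss concerns a comparison between arms, while the stated aims are within-arm, and it assumes that each user contributes nothing. The missing medication item is weak evidence: this is a short protocol without case report forms, so an unlisted item does not show that use goes unrecorded.

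**Conclusion.** The observation is correct as a matter of missing detail, but it does not call for a change to the design, endpoints or analysis. Background use creates no systematic bias between arms. For one or two users among 10 completers it shrinks a 3-point within-arm change by at most 0.30 or 0.60 points, against a half-width of 1.43 points at the smallest SD considered. The direction and scale rest on assumptions: the user count (possibly zero), the SD and the response of prior users are all absent from the documents, so no firm numerical effect on the primary aims can be derived.

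Analysts would fill the gap in the ordinary way, by listing baseline use of both drugs by arm and noting use at the existing visits. A prespecified analysis without users would be a small descriptive subset that alters no planned result.

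The wording of Exclusion Criteria 2 and 3, the metformin regimen in Design & Methods and the delay argument in Background should be reconciled by the sponsor for women already taking either drug. That is a clarification of text, and no dose or clinical rule is suggested here.

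### Only insulin-dependent diabetes is excluded, but the case for delaying metformin by 12 weeks covers only women who have not yet developed diabetes

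*Combined protocol and SAP*

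**What the plan says.** **Eligibility.** Exclusion Criteria, item 4, reads "Insulin-dependent diabetes mellitus". Inclusion Criteria, item 3, requires "Insulin resistance as evidenced by HOMA-IR > 2.0, calculated from fasting glucose and insulin". Two other exclusions bear on the point without naming diabetes: item 2, "Current metformin use of > 1gm daily", and item 8, "Other major medical comorbidity: renal or hepatic dysfunction, severe pulmonary disease". Item 9 is a discretionary clause on safety and data quality: "Presence of a condition or abnormality that in the opinion of the Investigator would compromise the safety of the patient or the quality of the" (cut before its last word). Under Design & Methods, "Subjects who meet all inclusion criteria and none of the exclusion criteria will be entered into the study", with 1:1 allocation to vitamin D or metformin for 12 weeks.

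**Rationale for the delay.** The last paragraph of the Background argues that a "delay of 12 weeks for treatment of insulin resistance will not likely predispose to rapid development of diabetes mellitus, the primary indication for treatment". Standard Clinical Practices says of insulin resistance shown by HOMA-IR that it is "believed to be an early stage of impaired glucose tolerance, metformin is another option we discuss". The same section names, as the long-run metabolic risk, progression to pre-diabetes or diabetes.

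**Mitigations.** Standard Clinical Practices says that every patient is counselled on diet and exercise, and that insulin resistance and vitamin D status are rechecked at the 3-month visit, when treatment is prescribed on the result.

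**The concern.** A trial that withholds one of two treatments needs a safety argument that covers everyone it can randomise. Here the argument treats diabetes as a future event that 12 weeks is unlikely to hasten. That is informative for a woman without diabetes and silent about a woman who already has it. By naming a single subtype, the exclusion list leaves the others eligible.

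What is at stake is participant safety and the coherence of the ethical justification. A woman with untreated non-insulin-dependent diabetes could be assigned vitamin D and have the start of metformin put off for 12 weeks on a justification that does not address her.

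**Working it through.** The documents give no figure on this point to reproduce. The check is to take a woman with untreated or newly detected non-insulin-dependent diabetes who otherwise qualifies, and test her against each relevant provision.

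| Provision | Effect on her |
|---|---|
| Inclusion 3 (HOMA-IR > 2.0) | A lower limit only; no upper limit on HOMA-IR or glucose |
| Exclusion 2 (metformin > 1 g daily) | Does not apply; she takes none |
| Exclusion 4 (insulin-dependent diabetes) | Does not apply |
| Exclusion 8 (major comorbidity) | Names renal, hepatic and severe pulmonary disease; diabetes is not listed |
| Exclusion 9 (investigator's opinion) | May be used; neither mentions diabetes nor requires exclusion for it |
| Entry rule (Design & Methods) | Enters her if none of the exclusions applies |
| Allocation 1:1 | Vitamin D with probability 1/2 |

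Only item 9 can stop her, and only by individual judgement.

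**Does the rationale reach her?** The Background speaks of diabetes developing. Standard Clinical Practices speaks of an early stage and of progression. Neither says anything about delaying metformin in a woman whose diabetes is already present.

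**Does the HOMA-IR criterion screen her out?** It works the other way. The documents give no formula, so I assume the usual one: HOMA-IR = fasting glucose (mg/dL) × fasting insulin (µU/mL) / 405. The insulin at which HOMA-IR reaches 2.0 is then 2.0 × 405 / glucose:

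- glucose 100 mg/dL (the impaired-fasting-glucose cut-off in Standard Clinical Practices): 810 / 100 = 8.1 µU/mL
- glucose 130 mg/dL (assumed example): 810 / 130 = 6.2 µU/mL
- glucose 160 mg/dL (assumed example): 810 / 160 = 5.1 µU/mL

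The higher the glucose, the less insulin is needed to qualify. This shows direction only. It does not say what share of women with diabetes would qualify, because the documents give no insulin distribution.

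**How many?** If k such women were randomised, k/2 would be expected in the vitamin D arm. The documents give nothing from which to estimate k, and it may be zero.

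**The case against.** The strongest reply is that safeguards already exist. Item 9 squarely permits exclusion of a woman with a worrying glucose. The safeguard has a practical basis: fasting glucose must be known to compute HOMA-IR, screening data are reviewed for eligibility, and reproductive endocrinologists see the clinic's patients. This stands as mitigation. It does not close the gap, because item 9 is optional and two investigators could apply it differently to the same result.

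Second, every patient has a lifestyle intervention and a 3-month recheck, and Standard Clinical Practices lists lifestyle alongside metformin as an option for raised glucose. This also stands in part. But the counselling is offered against insulin resistance rather than established diabetes, and the recheck comes when the delay is over.

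Third, neither section states that no participant has diabetes, and the Background sentence could mean that preventing diabetes is the main reason to treat. Both remarks are fair: the restriction to women without diabetes is inferred from the wording. On either reading, though, existing diabetes is not addressed.

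Fourth, a reader might infer that every woman with diabetes not on insulin has treatment withheld. The documents do not support that. Item 2 removes those on more than 1 g of metformin daily, and nothing requires other glucose-lowering drugs to be stopped. The documents do not say whether metformin at or below that level continues in the vitamin D arm. The point is therefore confined to untreated or newly detected diabetes.

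**Conclusion.** The concern holds as a mismatch between the written eligibility criteria and the written justification for delay. A woman with untreated or newly detected non-insulin-dependent diabetes may be randomised, and with probability 1/2 assigned vitamin D, without the delay rationale covering her, unless the investigator chooses to use item 9. The conclusion rests on the text of the criteria and on reading the rationale as concerned with development and progression. It does not depend on the assumed HOMA-IR formula or on the example glucose values.

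The number of women affected is unknown. It would be tempting to infer that such women would cross over to metformin or lose their week-12 data, or that the HOMA-IR criterion admits nearly all of them. No section supports the first, and the second needs data that the documents do not contain. Nor do the documents show that any such woman was or will be enrolled. This is a gap on paper with a safety aspect, softened by existing safeguards and cheap to close.

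**What to change.** Reconcile Exclusion Criteria, item 4, with the delay argument in the Background and Standard Clinical Practices, so that the written criteria match the population which that argument describes. State that this is checked before randomisation, using the fasting glucose already obtained for HOMA-IR. Rewording the rationale alone would leave unchanged who is randomised. Which clinical rule to adopt, and how to define it, is for the investigators.

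The cost is an amendment to one criterion, with no new test. The downside is possibly a few fewer eligible women against a recruitment target of 25.

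### The final BDI-II evaluation is tied to completing treatment and the SAP does not say who is analysed, so a literal reading leaves a completer result that dropout can bias

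*Combined protocol and SAP*

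**What the plan says.** The Sample Size Calculations paragraph starts from a calculated 8 per group and raises this: "we aim to have 10 subjects per group complete the trial, for a total of 20". It then allows for losses: "Assuming 20% attrition, we will recruit 25 subjects to result with 20 in total". DESIGN & METHODS gives the same target: "Twenty-five subjects will be enrolled in order to have 20 subjects complete the study with roughly 10 subjects in each treatment regimen arm".

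The visit schedule in DESIGN & METHODS reads: "Evaluations will be completed at baseline, after 6 weeks, and after completing 12 weeks of treatment". The Project Summary confirms that depression severity is measured at baseline, at 6 weeks and at the end. No section describes an evaluation for a randomised woman who stops her assigned treatment before week 12.

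The Statistical Analysis Plan paragraph refers to models with optional covariates. It does not name the analysis population, the primary time point, the form of the model, a method for missing BDI-II scores or any use of the week-6 score. Both primary aims under OBJECTIVES concern change within an arm. A comparison between arms is implied by the randomisation and the sample-size text, but no such test is written out.

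**The concern.** Three features combine. The last evaluation is worded as following completed treatment, the target is a number of completers, and no rule covers the five women expected to be lost. Taken at face value, this produces an analysis of completers. At best, the choice of who counts is left until the data have been seen, in an open-label trial.

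Two estimates are at stake:

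- **Within-arm change.** If women who are not improving leave, the remaining women show more improvement than the arm as randomised. Equal dropout in the two arms does not cure this, because nothing cancels within one arm.
- **Arm contrast.** The comparison is biased when dropout differs between arms in rate or in reason. The arms differ in treatment burden (a stepped, twice-daily regimen against one daily tablet) and participants know their assignment. A difference is therefore plausible, though not established.

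A week-6 BDI-II is already planned for everyone and could recover part of what is lost, but the plan gives it no stated role.

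**Working it through.** **1. The plan's own figure.** Inputs: 20 completers and 20% attrition (Sample Size Calculations). Formula: N = completers / (1 − attrition) = 20 / 0.80 = 25. This reproduces the stated 25. Expected losses are 25 × 0.20 = 5. The inflation is correct and is not the problem.

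**2. Hand calculation of bias.** In one arm, completer mean minus full-arm mean = −(dropout rate) × (dropout mean − completer mean). The documents do not give the gap between dropouts and completers, so it is assumed.

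- Within one arm, 20% dropout and gaps of 3, 5 or 8 points: 0.20 × 3 = 0.6, 0.20 × 5 = 1.0, 0.20 × 8 = 1.6 points of spurious improvement.
- Contrast, 30% informative dropout in one arm and random dropout in the other, gap 5: 0.30 × 5 = 1.5 points. Random dropout adds no bias, so the other arm's rate is not subtracted.
- Contrast, 30% and 10% dropout, informative in both arms with the same gap of 5: (0.30 − 0.10) × 5 = 1.0 point.
- Contrast, same rate and same gap in both arms: 0.

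**3. Simulation of the arm contrast.** Assumptions, none of them in the documents: 12 and 13 randomised; no true effect; about 30% dropout linked to poor week-6 change in one arm and 10% at random in the other (about 20% overall); BDI-II SD 6 to 9; correlation between adjacent visits 0.60 to 0.75. The strength of the link between week-6 change and dropout is also assumed; where stated, it was a logit slope of 1.5 per SD.

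| Analysis | Bias in week-12 contrast (points) |
|---|---|
| Completers, adjusted for baseline | about 0.7 to 1.4, favouring the high-dropout arm |
| All randomised, using week 6, every dropout has a week-6 score | about 0.1 or less |
| All randomised, using week 6, half of dropouts leave before week 6 | about 0.3 to 0.6 |

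Against the 3-point threshold in the Sample Size Calculations, completer bias is 0.7 / 3 = 23% to 1.4 / 3 = 47%. The standard error of the contrast is 2.3 to 3.9 points, so the bias is roughly 0.3 to 0.4 of a standard error. A nominal 5% test rejects about 6% to 7% of the time.

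**4. Sensitivity.** With SD 6 to 10, correlation 0.5 to 0.85 and informative dropout in one arm only:

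- 20% dropout in each arm gives 0.7 to 1.9 points, so equal rates alone do not protect the contrast.
- 32% against 8% gives 1.1 to 3.0 points.
- If half of the dropouts leave before week 6, using week 6 still leaves 0.3 to 1.2 points over these settings.

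**5. Within-arm change.** With 20% dropout linked to poor week-6 change and no true change, simulated completers show a spurious improvement of about 0.9 to 1.5 points. This agrees with the range in step 2.

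**6. Random dropout.** If dropout is purely random there is no bias, and using week 6 makes the standard error only 1% to 3% smaller. The case for the change rests on bias, not precision.

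**The case against.** The strongest reply is that this reads intent into silence. A reader might infer that the plan prescribes a completer analysis and discards the week-6 scores. The documents support neither inference. Recruiting 25 to retain 20 is ordinary inflation and commits the trial to no analysis set, and the unspecified models neither include nor exclude week 6. The schedule wording may simply be a way of naming the week-12 visit. The Project Summary speaks of completing the protocol, and Standard Clinical Practices describes a routine 3-month clinic visit. That visit is not said to include the BDI-II, however, and no section says that women who stop treatment will be evaluated. The gap in the schedule therefore stands, as a matter of what the text says and omits.

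It can also be said that every bias figure rests on assumed dropout patterns and that 20% attrition overall does not show a difference between arms. Both points are correct. With about 20 completers, imprecision outweighs the bias.

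Using week 6 is not a complete remedy. It works when dropout depends on observed scores. The metformin titration described in DESIGN & METHODS falls in the first weeks, and a loss at that stage would precede the week-6 score.

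Finally, the primary aims are within-arm, and the trial is a pilot. This rules out treating the arm contrast as the sole primary result. It does not remove the concern, because within-arm change among completers is biased even when both arms lose women alike.

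**Conclusion.** The concern holds as a gap with a foreseeable consequence. The schedule wording, the completer target and the missing analysis rules together lead, if followed literally, to a result based on women who finished treatment. Under the stated assumptions the completer contrast is off by about 0.7 to 1.4 points. That is material against a 3-point threshold but modest beside a standard error of 2.3 to 3.9 points. It falls to zero if dropout has the same rate and reasons in both arms. Within-arm change is biased whenever dropout is linked to poor response, by about 0.9 to 1.5 points at 20% dropout under the assumptions used.

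It would go too far to conclude that the trial has chosen a completer analysis, that the week-6 data will be ignored, or that unequal dropout is to be expected. The plan should be changed because the remedy is cheap and the choice should be fixed before the data are seen. Confidence in the size is moderate, since the documents give no SD, no correlation and no dropout pattern.

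**What to change.** 1. **DESIGN & METHODS, visit schedule.** State that the final questionnaires are collected 12 weeks after randomisation from every randomised woman, whether or not she completed treatment. This matters most, because week-6 data cannot help for a woman who leaves before week 6.

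2. **Statistical Analysis Plan paragraph.** State that all randomised women are analysed in their assigned arm, with a mixed model for BDI-II at weeks 6 and 12 containing arm, visit, arm-by-visit and baseline BDI-II. Report week-12 change within each arm, in line with the primary aims, and the week-12 arm contrast. Give the completer analysis as a sensitivity analysis.

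**Cost.** A few sentences in two places and a small effort to obtain questionnaires from women who have stopped treatment. The number recruited stays at 25 and treatment is unaffected. The model relies on dropout depending on observed scores. The fewer final questionnaires are missing, the less that assumption has to carry.
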